A statistician prepared a sampling design that included three configuration diagrams. Each diagram identified five implants of the three types, and showed how one of each type was to be placed in a cyclical, side-by-side, rotating fashion at five sites between mental foramen. In this way, an equal number of each implant type was to be placed at each of the five sites, and an equal number of participants received three of the five implants to the left or right of the midline. Configuration diagrams also documented each implant's length. Allocation concealment by the project coordinator then allowed 20 participants to receive Configuration 1, 19 had Configuration 2, and 19 had Configuration 3. Configuration diagram (but not number) was stored inside each chart, and only shown to the operating team at the time of surgery. The same surgeon ([name]) placed all implants, in a submerged fashion, with MG at the crest. Implants were 3.75mm in diameter, but the project coordinator determined implant length based on pre-operative radiographic measurements of available bone height. After approximately six months, the same surgeon exposed all implants, removed cover screws, and placed healing/prosthetic abutments. Complete seating of abutments onto implant platforms was confirmed with radiographs. Each participant received a conventional complete removable maxillary prosthesis and a fixed implant-supported mandibular prosthesis with bilateral posterior cantilever sections. Acrylic-resin teeth were processed over a casted, silver-palladium alloy framework. Gold prosthetic screws for Brånemark® and Swede-Vent® implants, and titanium screws for Screw-Vent® implants anchored the mandibular prostheses to the abutments. Participants followed an oral/implant hygiene regimen of daily mouthwash rinses, and gentle flossing and brushing with provided hygiene kits. Follow-ups occurred at one year, two years, 15 to 20 years, and 23 to 26 years

following prostheses attachment. Twenty-two participants (41.5%, age 71.1 ± 1.2 years, 11 women, 110 implants) were enrolled in the present study

Clinical and radiographic evaluation

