Assessment was initially based on intention-to-treat. Based on a previous study (Camarda, et al., 2018), the effect size for the difference in bone level change between implant groups was expected to be 0.95. A sample size of 16 participants would, therefore, ensure an 80% power to reject the null hypothesis, if it was indeed false at a two-sided Bonferroni-adjusted α level of 0.017 (to adjust for pairwise comparisons between implant groups), using a repeated measures ANOVA. Absence or presence of prosthesis, abutment, and implant mobility was analyzed with the Fisher's exact test. The mean keratinized gingiva height (mm), probing depth (mm), and percentage of sites with dPI, dBI and purulence were calculated for each implant. Shapiro-Wilk test was used to assess the normality of data distribution. These values were then analyzed with nonparametric ANOVA-type statistic for repeated measures within subject, with implant type, site and configuration as independent variables (Brunner, et al., 2002). Quantitative bone healing was analyzed with mixed models for repeated measures within subject, with implant type, site and configuration as independent variables, and implant length as covariate. The lengths of the different implant types were compared with a Kruskal-Wallis test. Confidence Interval (CI) was established at two-sided 95% Confidence Level (CL). The level of significance was set at $p < 0.05$ and Bonferroni correction was applied for pairwise comparisons. ICC (two-way, mixed-effect model) and Bland-Altman limits of agreement (Bland, & Altman, 1986) were used to analyze comparison of mean fBIC-MG values between conventional peri-apical radiology and phosphor-plate technology. All statistical analyses were performed using IBM SPSS Statistics for Windows® Version 25 (IBM Co., Armonk, NY, USA), and SAS 9.4 (SAS Institute, Cary, NC, USA).

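### Do 95% confidence intervals conflict with Bonferroni-corrected pairwise tests at 0.017?

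*Combined protocol and SAP*

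**What the plan says.** All the relevant statements but two are in the *Statistical methods* section of the combined protocol and SAP.

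- Confidence level: "Confidence Interval (CI) was established at two-sided 95% Confidence Level (CL". No estimate or analysis is named.
- Significance: the next sentence sets the level at p < 0.05 and adds that "Bonferroni correction was applied for pairwise comparisons".
- Sample size: the calculation uses a "two-sided Bonferroni-adjusted α level of 0.017 (to adjust for pairwise comparisons between implant groups". This is the only place where a per-comparison level is written out.
- Bone level, the outcome for which model-based pairwise differences would be estimated: "Quantitative bone healing was analyzed with mixed models for repeated measures within subject".

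The other two are in *Initial study design, surgical and prosthetic treatments*. The configuration diagrams fix the number of comparisons ("Each diagram identified five implants of the three types", hence three pairs), and the section gives 22 participants and 110 implants at this follow-up.

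**The concern.** The correction is attached to the comparisons, while the interval sentence stands alone with one level and no exception. Read literally, each pairwise test is decided at 0.0167 while the interval for the same difference is drawn at 95%. Any unadjusted p-value between 0.0167 and 0.05 would then come with an interval that excludes zero and a test that is not significant.

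This would matter most for bone level. The pairwise contrasts there separate the two design features: Screw-Vent and Swede-Vent share the etched surface and differ in collar, while Swede-Vent and Brånemark share the collar and differ in surface. Readers will look to those intervals for the size of the collar effect. Three uncorrected, unlabelled intervals could be taken as a second and more lenient decision rule than the one used to size the study.

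**Working it through.** **Inputs.** From the plan: three implant types, so 3 pairs; nominal significance 0.05; two-sided per-comparison level 0.017; effect size 0.95; planned n = 16 with 80% power; 22 participants available. Assumptions: the effect size is standardised by the SD of within-participant differences, and each contrast behaves like a paired t-test. The mixed model's degrees of freedom are not given, so results are shown from 15 df (n = 16) to the normal limit, with 21 df for n = 22.

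**1. The plan's own figures.** 0.05/3 = 0.01667, which rounds to the stated 0.017. Exact noncentral-t power for a paired contrast, with noncentrality 0.95 × √n and two-sided α = 0.017, is 78.0% at n = 14, 81.9% at n = 15 and 85.2% at n = 16. The smallest adequate n is 15, against the stated 16. That is close enough to show that the study was sized on corrected pairwise tests.

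**2. Interval width.** An interval matched to a test at 0.05/3 has level 1 − 0.01667 = 98.33%. The width ratio is t(1 − 0.05/6) / t(0.975):

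| df | 95% critical value | 98.33% critical value | ratio | 95% interval narrower by |
|---|---|---|---|---|
| 15 | 2.131 | 2.694 | 1.264 | 20.9% |
| 21 | 2.080 | 2.601 | 1.251 | 20.1% |
| 42 | 2.018 | 2.494 | 1.236 | 19.1% |
| normal | 1.960 | 2.394 | 1.221 | 18.1% |

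**3. Joint coverage.** In 100,000 simulated data sets with n = 22 and one value per implant type per participant, three paired 95% intervals all covered the truth in 87.5% of runs. Three 98.33% intervals did so in 95.4%. With normal critical values the first figure is 87.8%.

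**4. Chance of disagreement.** For one comparison, the probability that an uncorrected 95% interval excludes zero while the corrected test is not significant equals power at 0.05 minus power at 0.01667:

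| true standardised effect | n = 16 | n = 22 |
|---|---|---|
| 0 | 3.3% | 3.3% |
| 0.4 | 14.9% | 17.3% |
| 0.5 | 18.5% | 19.2% |
| 0.95 (planned) | 9.4% | 2.9% |

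For example, at n = 22 and 0.95: 98.88% − 95.98% = 2.90%. Under the null: 5.00% − 1.67% = 3.33%.

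**5. What the text commits to.** Steps 2 to 4 apply only if pairwise intervals are reported and left uncorrected, and the section states neither. The 95% level and the 0.05 level stand in adjoining sentences. The 0.05 is plainly a nominal level to which the pairwise correction is then applied. Reading the 95% the same way gives 98.33% per pair, and the mismatch disappears.

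**6. Scope.** Mobility, implant length and the soft-tissue outcomes are described as tests (Fisher's exact, Kruskal-Wallis, nonparametric ANOVA-type statistic), with no interval for a pairwise difference mentioned. The ICC and limits of agreement compare radiographic methods and lie outside the three-way implant comparison. Only the bone-level contrasts are clearly exposed.

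**The case for a change.** The strongest argument for a change is that the plan names an adjusted level when it means one, as in the sample-size sentence, and names none for intervals. The natural reading is then 95% for every interval. If two readings give intervals differing in width by about a fifth, the interval is not fully specified, and a single sentence would settle it. The risk of disagreement is also not negligible at moderate effects: about one in five for a comparison at a standardised effect of 0.5.

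Part of this stands. The text is silent on the point, the widths do differ by that much, and uncorrected intervals shown without a label beside corrected tests could mislead.

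It does not follow that the plan is wrong. A 95% interval is too narrow only against a promise of joint coverage or of exact agreement with the corrected test, and the plan makes neither. Corrected tests reported with individually valid, labelled 95% intervals are a legitimate choice; simultaneous 98.33% intervals are another, at the price of width. Requiring the second would replace one defensible convention with another. Nor would it help to adopt 98.33% while keeping 95% for a single primary contrast tested at 0.05: the documents define no such contrast, and the correction is stated for pairwise comparisons without exception.

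**Conclusion.** No change to the plan is needed. The arithmetic holds, but the contradiction depends on a choice that the document does not state, and on either reading the analysis is sound. Uncorrected 95% intervals would be 18% to 21% narrower than test-matched ones over the degrees of freedom considered, and corrected ones would match the tests. Neither choice alters the sample size, any test decision or any point estimate.

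The missing detail is a matter of labelling for the bone-level contrasts: the report should say whether each pairwise interval is Bonferroni-adjusted or an unadjusted 95% interval. A competent analyst supplies that as routine. The conclusion rests on the corrected tests remaining the decision rule, as the plan sets them, and on the paired-t approximation used for the probabilities above.

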After having assured the stability of all abutments, radiographic evaluation of quantitative peri-implant bone healing was performed with the conventional peri-apical technique, using a standardized equipment and measurement protocol (Camarda, et al., 2018). Five peri-apical radiographs per participant were taken and numbered according to the implant site, 1 being the first on the subject's left, 5 the last on the right, and were stored in plastic film holders. In order to compare and calibrate conventional peri-apical radiology with phosphor-plate technology, the Digora System™ (Digora Optime™, Sporedex Dental Co., Tuusula, Finland) was also used with the standardized equipment to take peri-apical radiographs on 95 implant/abutment units (Bhasharan, et al., 2005). Following calibration, the distance between the first-bone-to-implant-

contact-point and the crestal-microgap (fBIC-MG) was measured (mm) at the mesial and distal aspects of each implant/abutment unit using a Schei ruler under X10 magnification on the conventional films. Adobe Photoshop® (Adobe System Incorporated, San Jose, CA, USA) was used to measure fBIC-MG on the digital radiographs acquired with phosphor-plate technology. After having taken the radiographs, all abutments were removed and cleaned, and prosthesis/framework structures were cleaned and polished. Abutments and prosthesis/framework structures were then re-inserted using recommended instrument torque. Intraclass Correlation Coefficient (ICC, two-way mixed-effect model) assessed inter-examiner and intra-examiner reliability of bone level measurement on 20 radiographs. The reliability was excellent, with an inter-examiner ICC of 0.94 and an intra-examiner ICC of 1.00. The Dahlberg measurement error was 0.38mm.

Statistical methods

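### The film-versus-phosphor-plate agreement analysis names no participant level for 95 implants from 19 to 22 mouths, so any intervals it yields are too narrow to the extent that differences correlate within a mouth

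*Combined protocol and SAP*

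**What the plan says.** Clinical and radiographic evaluation describes a side study that compares and calibrates conventional film against phosphor plate. The digital system was used "to take peri-apical radiographs on 95 implant/abutment units". Bone level (fBIC-MG) was "measured (mm) at the mesial and distal aspects of each implant/abutment unit", with a ruler on film and in image software on the digital images.

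The number of mouths follows from two other statements. Initial study design, surgical and prosthetic treatments reports: "Twenty-two participants (41.5%, age 71.1 ± 1.2 years, 11 women, 110 implants) were enrolled in the present study". Clinical and radiographic evaluation adds: "Five peri-apical radiographs per participant were taken and numbered according to the implant site".

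Statistical methods names the analysis: "ICC (two-way, mixed-effect model) and Bland-Altman limits of agreement", the latter with a 1986 reference, "were used to analyze comparison of mean fBIC-MG values between conventional peri-apical radiology and phosphor-plate technology". It does not say at what level the mean is taken. The same section sets a general two-sided 95% confidence level without tying it to this comparison. For the outcome it is explicit about dependence: "Quantitative bone healing was analyzed with mixed models for repeated measures within subject". The clinical indices are likewise analysed within subject.

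**The concern.** Implants in one mouth share a patient and probably a recall session, so their film-minus-plate differences may be alike. A two-way ICC model has two factors, the measured unit and the technique; participant would be a third. The basic limits of agreement use a single standard deviation of the differences, and the usual standard errors for the bias and the limits treat those differences as independent. The plan allows for within-mouth dependence in its outcome models but names nothing comparable here.

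What is at stake is how precisely the agreement between the two techniques is known. With short intervals, a systematic difference between film and plate could look better established than it is, or the limits and the ICC could look more certain than they are.

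**Working it through.** **The plan's own figures.** No design calculation is given for the agreement study. The only one concerns the bone-level comparison: 16 participants, effect size 0.95, two-sided alpha 0.017, 80% power. Taking 0.95 as the standardised paired difference, an exact paired t calculation needs 15 participants (power 0.819) and gives power 0.852 at 16. So 16 is slightly conservative, and it does not depend on the agreement study.

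**Number of mouths.** 110 implants / 22 participants = 5 per mouth. At least 95 / 5 = 19 mouths are needed to supply 95 units, and at most 22 are available.

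**Assumptions.** One value per implant (mesial and distal averaged) enters the analysis. The differences have within-mouth correlation rho. The documents do not give rho, so a range starting at zero is used.

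**Formula.** Design effect = 1 + (mA - 1) x rho, with mA = sum(m^2) / sum(m) and m the number of units in a mouth. Effective n = 95 / design effect. The standard error of the bias is understated by the square root of the design effect.

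- 19 mouths of five: mA = 5. At rho = 0.3, design effect = 1 + 4 x 0.3 = 2.2 and effective n = 95 / 2.2 = 43.
- 22 mouths (7 with five units, 15 with four; 35 + 60 = 95): mA = (7 x 25 + 15 x 16) / 95 = 415 / 95 = 4.37. At rho = 0.3, design effect = 1 + 3.37 x 0.3 = 2.01 and effective n = 47.

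Coverage comes from 20,000 simulated data sets of 19 mouths of five, using the independent-data formulas: s / sqrt(N) for the bias and sqrt(3) x s / sqrt(N) for a limit, where s is the standard deviation of the differences and N = 95.

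| rho (assumed) | 0 | 0.1 | 0.2 | 0.3 | 0.5 |
|---|---|---|---|---|---|
| Design effect, 19 x 5 | 1.00 | 1.40 | 1.80 | 2.20 | 3.00 |
| Effective n, 19 x 5 | 95 | 68 | 53 | 43 | 32 |
| SE of bias understated by factor, 19 x 5 | 1.00 | 1.18 | 1.34 | 1.48 | 1.73 |
| Effective n, 22 mouths | 95 | 71 | 57 | 47 | 35 |
| SE of bias understated by factor, 22 mouths | 1.00 | 1.16 | 1.29 | 1.42 | 1.64 |
| Coverage of 95% interval for bias, 19 x 5 (about) | 95% | 90% | 86% | 81% | 74% |
| Coverage of 95% interval for a limit, 19 x 5 (about) | 95% | 93% | 91% | 88% | 80% |

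**Point estimates.** The estimated standard deviation of the differences averages 0.997 of its true value at rho = 0 and 0.983 at rho = 0.5. The limits therefore hardly shift.

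**ICC.** The result also depends on the within-mouth correlation of true bone levels. With an assumed true ICC of 0.94 and 4,000 simulations, the usual interval covers about 95% with no clustering. It covers about 92% with correlations of 0.3 (true levels) and 0.2 (errors), and about 85% with 0.5 for both.

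**The case against.** The text does not say that the units were treated as independent; that is inferred from the methods named. If the means compared were participant means, the criticism would fall away. This stands as a reason for conditional wording. A mean per implant is still the natural reading, because the sample is described in implant units and the clinical indices are averaged per implant. If mesial and distal readings were entered separately (2 x 95 = 190), the dependence would be stronger.

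A reader might infer that the study's reported intervals are too narrow. The documents do not support that: they describe no interval for the bias, the limits or this ICC, only a general 95% level.

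The correlation is also unknown and could be small. Anatomy that affects both images of an implant equally cancels in the difference, and image-by-image reading error (a Dahlberg error of 0.38 mm is reported) need not correlate within a mouth. The documents do not say that angulation or sensor fit is shared across a mouth's five exposures. At zero correlation there is no shortfall. This stands, and is why a range is shown.

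It would be tempting to say that the 1986 reference itself requires one difference per subject. That source is not in the documents, so nothing here rests on it.

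Finally, a reader might infer that the implant-type comparison is weakened. The documents show no route to it: bone healing was evaluated on conventional film, its model already works within subject, and no agreement threshold or decision rule is attached to the calibration. This part of the objection stands in full.

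**Conclusion.** The point holds in conditional form. That the units are clustered, and that the named agreement methods have no participant level, can be read from the documents. That any intervals would be too narrow depends on two assumptions: one mean per implant enters the analysis, and the differences correlate positively within mouths. For correlations of 0.1 to 0.5, across both layouts, the naive interval for the bias would be about 14% to 42% narrower than standard errors allowing for clustering would give (1 - 1/1.16 to 1 - 1/1.73). The issue is precision only, in a secondary calibration analysis. Severity is minor, but since a better method is available at almost no cost, this is more than a missing detail.

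**What to change.** State the unit of analysis: one mean of mesial and distal per implant, or separate readings with implant nested in participant. Also state how many participants contribute the 95 units.

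Fit the film-minus-plate difference with a random participant effect. Compute the limits as bias +/- 1.96 x sqrt(between-participant variance + within-participant variance). Take the intervals for the bias, the limits and the ICC from a bootstrap that resamples participants rather than implants. Reporting the two variance components would also show whether the within-mouth correlation matters.

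No new data are needed, and SAS 9.4, which the plan already names, can do this in a few lines. The price is somewhat wider intervals. As a guide, with 19 mouths of five and a t interval on 18 degrees of freedom, the interval for the bias would be 1.06 times the naive width at zero correlation, 1.25 times at 0.1 and 1.83 times at 0.5.
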